2.1.2. Endpoints

Primary Endpoints

For Part 1:

The primary endpoint is the PK of ALS-008112 and ALS-008144 (and other metabolites, if applicable) in plasma.

For Part 2:

The primary endpoint is RSV RNA viral load (measured by qRT-PCR in the mid-turbinate nasal swab specimens) AUC from immediately prior to first dose of study drug (baseline) until Day 7.

Secondary Endpoints

The secondary endpoints for Part 1 and Part 2 are:

- Safety/tolerability including AEs, physical examinations, vital signs, ECGs, and clinical laboratory results
- RSV clinical course endpoints:
 - Length of hospital stay from admission to discharge and from study treatment initiation to discharge.
 - Length of hospital stay from admission to readiness for discharge and from study treatment initiation to readiness for discharge, with readiness for discharge defined by the investigator.
 - Need for and duration of intensive care unit (ICU) stay.
 - Need for and duration of supplemental oxygen (regardless of method used).

-
- Number of hours until peripheral capillary oxygen saturation (SpO₂) ≥93% on room air among subjects who were not on supplemental oxygen prior to the onset of respiratory symptoms.
 - Respiratory rate, SpO₂, and body temperature return to pre-RSV disease level.
 - Need for and duration of noninvasive ventilator support (eg, continuous positive airway pressure) and/or invasive ventilator support (eg, endotracheal-mechanical ventilation or mechanical ventilation via tracheostomy).
 - Time to return to pre-RSV functional status (Katz ADL score).
 - Need for hydration and feeding by IV catheter/nasogastric tube.
 - Time to clinical stability defined as the time at which the following criteria are all met:
 - normalization of blood oxygen level (return to baseline; by pulse oximetry) without requirement of supplemental oxygen beyond baseline level
 - normalization of oral feeding
 - normalization of respiratory rate
 - normalization of heart rate
 - Improvement on the ordinal scale.
 - All-cause mortality.
 - RSV RNA viral load as measured by qRT-PCR of the mid-turbinate nasal swab specimens which will be used to determine the following:
 - Viral load over time.
 - Peak viral load, time to peak viral load, rate of decline of viral load, and time to RSV RNA being undetectable.
 - Proportion of subjects with undetectable viral load at each time point.

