 - The RSV RNA viral load AUC from immediately prior to first dose of study drug (baseline) until Day 7 (secondary for Part 1 only).
 - RSV RNA viral load AUC from immediately prior to first dose of study drug (baseline) until Day 10 and until Day 14.
 - RSV RNA viral load AUC in subjects assigned to a longer dosing duration, if dosing duration is increased by the IDMC, from baseline until 1 day after the last dose of study drug (Part 2 only).
 - Sequence changes (postbaseline) in the RSV polymerase L-gene and other regions (only if no mutations are seen in the L-gene) of the RSV genome compared with baseline sequences.
 - Population-derived PK parameters of ALS-008112.

Exploratory Endpoints

The exploratory endpoints for Part 1 and Part 2 are:

- The amount of:
 - Supplemental oxygen above pre-RSV disease level (regardless of method used) from study treatment initiation to Day 7.
NOTE: If the dosing duration is increased by the IDMC to up to 10 days, supplemental oxygen above pre-RSV disease level will be measured from treatment initiation until 1 day after the last dose of study drug.
 - Oxygen delivered by noninvasive ventilator support (eg, continuous positive airway pressure) and/or invasive ventilator support (eg, endotracheal-mechanical ventilation or mechanical ventilation via tracheostomy).
 - Subjects (proportion) who started antibiotic use after the first dose of the study drug.
- Disease status and presence of complications with onset after treatment initiation:
 - Bacterial superinfections reported as AEs (eg, pneumonia, acute otitis media, sinusitis, bronchitis, bacteremia).
 - Exacerbations of underlying pulmonary disease (eg, asthma, chronic obstructive pulmonary disease).
 - Cardiovascular and cerebrovascular events (eg, myocardial infarction, congestive heart failure exacerbation, arrhythmia, stroke).
 - Respiratory failure.
 - *Clostridium difficile* associated diarrhea.
 - Other RSV-related complications.
- Duration and severity of signs and symptoms of RSV infection as assessed by the respiratory infection patient-reported outcome (RI-PRO) questionnaire and additional questions about health and functioning completed by the subject in the eCOA.
- HRQoL assessed by the EuroQoL 5 Dimension 5 level version (EQ-5D-5L) completed by the subject in the eCOA.
- Hospital readmission for respiratory reasons up to the Day 28 follow-up visit.
- Medical resource utilization.

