11.3. Efficacy Analyses

Primary Endpoint

For Part 2, the primary endpoint in this study is RSV RNA log₁₀ viral load (measured by qRT-PCR in the mid-turbinate nasal swab specimens) AUC immediately prior to first dose of study drug (baseline) over 7 days. Mean log₁₀ viral load values over time will be analyzed using a restricted maximum likelihood based repeated measures approach. Analyses will include the fixed, categorical effects of treatment, strata, visit, and treatment-by-visit interaction, as well as the continuous, fixed covariates of baseline log₁₀ viral load and baseline log₁₀ viral load by-visit interaction. An unstructured (co)variance structure will be used to model the within-subject errors over time. The differences in the AUCs for active versus placebo will be derived using

appropriate contrasts deriving least square mean differences, including the 95% 2-sided confidence intervals. For inferential purposes, p-values will be compared with significance levels controlling for the (family-wise) type 1 error rate. Details will be provided in the SAP that will be finalized before the first formal interim analysis of Part 2.

Secondary Endpoints

The secondary endpoint of time to clinical stability is defined as the time at which the following criteria are all met:

- normalization of blood oxygen level (return to baseline, pulse oximetry) without requirement of supplemental oxygen beyond baseline level
- normalization of oral feeding
- normalization of respiratory rate
- normalization of heart rate

Normalization criteria will be specified in the SAP. Subjects for which no time point could be established (eg, withdrawal of informed consent before reaching the endpoint or no clinical stability at last observation) will be (right-) censored at the latest time point at which it could be established that clinical stability was not reached. The differences in time to clinical stability of active dose regimens versus placebo treatment will be estimated using a Cox proportional hazard model; as baseline covariates, stratification factors, absence/presence of other viral or bacterial infections, baseline \log_{10} viral load, and time from onset of first symptoms to treatment will be added. Treatment effect versus placebo will be reported, including 95% confidence intervals. In case the proportional hazards assumption is not satisfied, appropriate sensitivity analyses will be performed as detailed in the SAP.

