11.12. Independent Data Monitoring Committee

An IDMC will be established to monitor data in both parts of the study and will review data in an unblinded manner on a regular basis to ensure the continuing safety of the subjects enrolled in

this study and to evaluate whether efficacy objectives are met. A Sponsor Committee will also be established and will be responsible for identifying appropriate actions based on the recommendations of the IDMC as described in the IDMC charter.

The IDMC will meet periodically to review interim data. After the review, the IDMC will make recommendations to the Sponsor Committee regarding the continuation of the study. The details will be provided in a separate IDMC charter.

The IDMC will consist of at least 1 medical expert in the relevant therapeutic area and at least 1 statistician, 1 of whom will chair the committee. The IDMC responsibilities, authorities, and procedures will be documented in its charter. Other members may be required dependent on the nature of the interim analysis (refer to Section 11.11).

For Part 1, the IDMC will review the safety and PK data after approximately 12 subjects have completed treatment as per the IDMC charter. When approximately 24 subjects have completed the Day 14 follow-up visit, an unblinded primary analysis will be performed by the sponsor for review by the IDMC. For Part 2, the IDMC will review the safety data initially after approximately 12 subjects have completed treatment and when approximately 12 Japanese subjects have completed treatment to assess that treatment may safely continue in each arm and will continue to assess PK, efficacy, and safety during the conduct of the study. Enrollment will continue while the IDMC reviews the data unless otherwise instructed by the IDMC. The frequency of IDMC reviews will be detailed in the IDMC charter.

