1.4. Sample Size Justification

The primary endpoint in this study is the AUC of the RSV RNA \log_{10} viral load over 7 days (or up to 11 days if the dose duration is extended up to 10 days).

The primary hypothesis is a positive dose-response relationship for the AUC of active treatment regimens. The positive dose-response relationship assumes that dose regimens with higher exposure with respect to MD will have at least an equal or better effect on viral load. Therefore 2 contrasts will be tested at each of the interim analysis points and final analysis; a contrast with no difference between the 2 active regimens tested against placebo and a contrast with a positive linear dose-response relationship with respect to active regimens. With respect to multiple contrast testing, multiplicity will be controlled at the pre-specified (interim) alpha level by calculating adjusted p-values from the simulated distribution of the maximum or maximum absolute value of a multivariate t random vector (ie, using the correlation between the contrasts to optimally control for alpha).¹ The overall (family-wise) type 1 error rate of 2.5% (1-sided) will be adjusted for multiple testing due to formal interim analyses using an O'Brien-Fleming alpha spending function with 3 sequential tests (2 interim, 1 final).⁵ As based on 10,000 simulations a sample size of 90 subjects randomized in a 1:1:1 ratio (placebo: low-dose ALS-008176: high-dose ALS-008176) will offer approximately 90% power to detect a positive dose-response relationship as defined assuming an effect size of 0.77 using Cohen's d (ie, the effect size expressed as the ratio of the standard deviation of the AUC) and approximately 80% power assuming an effect size of 0.67 (Cohen's d). Based on the results of the ALS-008176 RSV human challenge study, these effect sizes were considered plausible.⁶

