4.2. EFFICACY

The efficacy analyses include the following primary, secondary and exploratory endpoints.

Primary endpoint

- RSV RNA \log_{10} viral load (measured by qRT-PCR in the mid-turbinate nasal swab specimens) AUC from immediately prior to first dose of study drug (baseline) until Day 7 (or up to 11 days if the dose duration is extended to up to 10 days).

Secondary endpoints

- RSV clinical course endpoints:
 - Length of hospital stay from admission to discharge and from study treatment initiation to discharge.
 - Length of hospital stay from admission to readiness for discharge and from study treatment initiation to readiness for discharge, with readiness for discharge defined by the investigator.
 - Need for and duration of intensive care unit (ICU) stay.
 - Need for and duration of supplemental oxygen (regardless of method used).
 - Number of hours until peripheral capillary oxygen saturation (SpO₂) $\geq 93\%$ on room air among subjects who were not on supplemental oxygen prior to current hospitalization.
 - Respiratory rate, SpO₂, and body temperature return to pre-RSV disease level.
 - Need for and duration of noninvasive ventilator support (eg, continuous positive airway pressure) and/or invasive ventilator support (eg, endotracheal-mechanical ventilation or mechanical ventilation via tracheostomy).
 - Time to return to pre-RSV functional status (Katz ADL score).
 - Need for hydration and feeding by IV catheter/enteral tube.
 - Time to clinical stability defined as the time at which the following criteria are all met:
 - normalization of blood oxygen level (return to baseline; by pulse oximetry) without requirement of supplemental oxygen beyond baseline level
 - normalization of oral feeding
 - normalization of respiratory rate
 - normalization of heart rate

- Improvement on the ordinal scale
- All-cause mortality.
- RSV RNA viral load as measured by qRT-PCR of the mid-turbinate nasal swab specimens which will be used to determine the following:
 - Viral load over time.
 - Peak viral load, time to peak viral load, rate of decline of viral load, and time to RSV RNA viral load being undetectable.
 - Proportion of subjects with undetectable viral load at each time point.
 - RSV RNA viral load AUC from immediately prior to first dose of study drug (baseline) until Day 10 and until Day 14.

Exploratory endpoints

- The amount of:

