4.2.3. Primary Efficacy Endpoint

4.2.3.1. Definition

The primary estimates of the AUC will be derived from a mixed model (see section 4.2.3.2 for the detailed specification). No imputations of missing data from nasal swabs post-baseline will be done in this model, as this mixed model would allow to make inferences under the *missing at random* assumption.

Note that for the primary endpoint the following rules apply:

- Only values as provided by the central lab will be used.
- Baseline (Day 1) is defined as the last measurement before first intake. In case a result is available that is no later than 1 hour after treatment initiation this may be used but only if no pre-treatment observation is available.
- If for the baseline assessment the central laboratory value is missing, the value that will be imputed is based on the average value as based on the analysis population (ITT-i, ITT or PP population).
- For all post-baseline days the RSV RNA viral load result of the swab that was performed at that day will be used, counting from the Day of first treatment which is defined as Day 1.
- In case multiple nasal swabs were taken on a single day the average on the log scale will be used as the value for that subject.

As a sensitivity analysis, descriptive statistics will be provided for the viral load AUC calculated by the trapezoidal summation rule, based on planned days of sampling (Baseline visit up till/including Day 7 visit, or up to 11 days if the dose duration is extended to up to 10 days), including the timepoints with (imputed) values available:

$$AUC_{0-7 \text{ days}} = \frac{1}{2} \sum_{i=1}^n (y_i + y_{i-1}) \times (t_i - t_{i-1})$$

where $i=1,2,3,\dots,n$ are the time points when post baseline samples are collected, y_i is the log 10 viral load at the time and t_i is the time in hours post baseline. y_0 is the baseline log 10 viral load. t_0 is time 0.

The following additional rules, on top of the rules of the primary analysis, will be applied to deal with missing values post-baseline before calculating the Viral load AUC:

- Missing value between baseline and day 7 will be imputed by intrapolation.
- If the last observations are missing, the last available observation will be carried forward. Unscheduled assessments will be included and will be eligible for carrying forward.

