4.2.3.2. Analysis Methods

Mean \log_{10} viral load values over time will be analyzed using a restricted maximum likelihood based repeated measures approach. Analyses will include the fixed, categorical effects of treatment, strata, visit, and treatment-by-visit interaction, as well as the continuous, fixed covariates of baseline \log_{10} viral load and baseline \log_{10} viral load by-visit interaction. An unstructured covariance structure will be selected. In case this model will not converge, the

following list of covariance structures will be applied and a selection will be based on the Akaike Information Criterion for those that do converge:

- Unstructured [UN]
- Ante-dependence [ANTE(1)]
- Heterogenous Toeplitz [TOEPH]
- Heterogeneous CS [CSH]
- Heterogeneous AR(1) [ARH(1)]
- Toeplitz [TOEP]

The Kenward-Roger approximation will be used to estimate denominator degrees of freedom.

The testing of the dose-response relation is based on the expectation that higher dose regimens will be at least as efficacious as lower dose regimens with respect to efficacy on the viral load over time. Therefore, two contrasts on the dose regimens have been selected that are consistent with this expectation: a contrast with no difference between the 2 active regimens tested against placebo and a contrast with a positive linear dose-response relationship with respect to active regimens. A multiple comparison approach will be taken testing the 2 contrasts combined versus placebo, adjusted for multiplicity.

The SAS mock code used to test the primary hypotheses will be as follows:

```
proc mixed data=viral_load;
  where avisitn in (2,3,4,5,6,7)
  class avisitn trt usubjid stratum;
  model logtiter = trt|avisitn stratum base|avisitn /ddfm=kr s;
  repeated avisitn/subject=usubjid type=un;
  lsmestimate trt*avisitn
  "Plateau" -4 2 2 -4 2 2 -4 2 2 -4 2 2 -4 2 2 -2 1 1,
  "Linear" -4 0 4 -4 0 4 -4 0 4 -4 0 4 -4 0 4 -2 0 2
  /divisor=4 adjust=simulate seed=3369 alpha=alpha* lower cl;
run;
```

The variable *trt* denotes the *placebo*, *low dose regimen*, and *high dose regimen* treatment groups, the *avisitn* variable denotes the swabbing visits at Days 2 through 7, and the *base* variable is the baseline log₁₀ viral load measured at Day 1.

The significance level of *alpha* (α^*) will have to be calculated based on the information fraction at the time of the test using the pre-specified O'Brien-Fleming (OBF) α spending function.

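### The SAP lets the primary viral-load AUC run to 11 days if dosing is extended and starts its age bands at 50; the protocol fixes Day 7 and enrols from 18

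*SAP*

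**What the plan says.** **Primary window.** Protocol 2.1.2 gives the Part 2 primary endpoint as viral load "AUC from immediately prior to first dose of study drug (baseline) until Day 7", and Protocol 11.3 as "AUC immediately prior to first dose of study drug (baseline) over 7 days". Neither has an extension clause. Among the secondary endpoints, Protocol 2.1.2 lists the viral load "AUC in subjects assigned to a longer dosing duration, if dosing duration is increased by the IDMC, from baseline" to one day after the last dose.

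The SAP differs in three places. Section 4.2 takes the primary AUC "until Day 7 (or up to 11 days if the dose duration is extended to up to 10 days"). Section 1.4 has "viral load over 7 days (or up to 11 days if the dose duration is extended up to 10 days"). Section 4.2.3.1 takes the trapezoidal AUC to the "Day 7 visit, or up to 11 days if the dose duration is extended to up to 10 days", although the formula beneath it is labelled for 0 to 7 days. The SAP's secondary list has AUCs to Day 10 and Day 14 but not the protocol's extended-dosing AUC. The primary model code in SAP 4.2.3.2 is restricted by "where avisitn in (2,3,4,5,6,7"), and no 11-day version is given.

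**Age.** Protocol 4.1 enrols from 18 years (or the legal age of consent), and Protocol 5 stratifies Part 2 as 18 to <65 and 65 or over. SAP 1.2 describes a population aged 50 or over. SAP 1.2, 1.5, 2.5, 4.2.4.2 (ordinal scale) and 4.2.5.3.2 (EQ-5D) use 50 to <65 and 65 or over.

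**The concern.** The window is a live question, because dosing may be lengthened during Part 2. Under Protocol 11.12 the IDMC "will review data in an unblinded manner on a regular basis to ensure the continuing safety of the subjects" and to judge efficacy. An extension that it recommends and the sponsor endorses can take effect with no protocol amendment. The protocol would then say Day 7, the SAP text up to 11 days, and the SAP code Days 2 to 7. The confirmatory test would have no single agreed estimand, and the choice could fall after unblinded data had been reviewed. The SAP also does not say how subjects treated before and after an extension would be combined in one window.

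The age conflict does not depend on an extension. A subject aged 18 to 49 is eligible and is randomized in the under-65 stratum, but fits neither SAP age category.

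**Working it through.** **1. The plan's own power figure.** Inputs from SAP 1.4 and Protocol 11.2: 90 subjects 1:1:1, one-sided 2.5%, two contrasts, O'Brien-Fleming spending over three looks, and Cohen's d of 0.77 (about 90% power) or 0.67 (about 80%).

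- Contrasts: plateau (−1, 0.5, 0.5) and linear (−1, 0, 1). Correlation = 1.5/√(1.5 × 2) = 0.866.
- Looks at 15, 23 and 30 per arm. The first is 45/3; the second is an assumption.
- Cumulative one-sided alpha: 0.0015, 0.0105, 0.025. Simulated critical values for the larger of the two t statistics: 3.33, 2.56, 2.22.
- Simulated power with both active arms at the stated d: 90.7% and 81.0%. With half the effect on the low dose: 80.7% and 68.7%.

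The stated power therefore reproduces if both active arms share the stated d. Restoring the Day 7 window and the protocol's age bands changes none of its inputs (alpha, N, allocation, d).

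**2. The two windows are different estimands.** With Day 1 as baseline and the option read as Day 11:

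- To Day 7: 7 − 1 = 6 days. To Day 11: 11 − 1 = 10 days.
- Beyond the protocol's end-point: 11 − 7 = 4 days, and 4/10 = 40% of the longer window.
- Code weights after the divisor of 4: 4/4 = 1 for each of Days 2 to 6 and 2/4 = 0.5 for Day 7, sum 5.5. Adding the half-weight for baseline gives 6 days.
- A daily 11-day version would need weight 1 on Days 2 to 10 and 0.5 on Day 11, sum 9.5 (10 with baseline). The SAP contains no such contrast.

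**3. What would be observed.** Without an extension, the Time and Events Schedule (footnote s) plans swabs on Days 1 to 7, 10, 14 and 28. With one, swabs are daily to one day after the last dose. For a subject treated before an extension, the last scheduled swab at or before Day 11 is Day 10. The final 11 − 10 = 1 day of 10 (10%) has no scheduled swab at its end. An AUC to Day 10 remains computable from SAP Table 1.

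**4. Illustration only.** The documents give neither the within-subject correlations nor the effect after Day 7. Assume compound symmetry of 0.5 or 0.8, or AR(1) of 0.7 or 0.9, and start from d = 0.67 at Day 7. The unadjusted 60-versus-30 power at Day 7 is 85%.

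| Effect after Day 7 | d to Day 11 | Unadjusted power |
|---|---|---|
| Constant | 0.68–0.78 | 86–94% |
| Fades linearly to zero by Day 11 | 0.53–0.62 | 67–79% |
| Zero | 0.43–0.49 | 48–60% |

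The range shows that the windows are not interchangeable. The conclusion does not rest on it.

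**5. Age statements in the SAP.** Section 1.2 has three, 1.5 one, 2.5 two, 4.2.4.2 one and 4.2.5.3.2 one: 3 + 1 + 2 + 1 + 1 = 8. Two describe the population (both in 1.2), and 8 − 2 = 6 are age bands.

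**The case against.** The strongest reply is that this is a labelling problem with limited reach.

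- **Only if dosing is extended.** The window clause bites only then, and it is written in advance and tied to a treatment change. The extension may also rest on other studies. This is true, but the clause exists for exactly that case, and it contradicts the protocol's placing of the extended-dosing AUC among the secondary endpoints.
- **The code is mock code** for the standard regimen, so its Days 2 to 7 are incompleteness and not a rival definition. This is fair as far as it goes. An 11-day primary analysis would still be unspecified.
- **Visit handling.** SAP 2.1 sets the analysis visit equal to the study day for daily assessments after Day 6, so daily swabs under an extension are covered. This stands. It creates no Day 11 record for subjects treated earlier. The Day 10 visit may run to Day 12, so some may be swabbed on Day 11, but that swab is labelled Day 10. The 10% figure refers to scheduled days.
- **Missing data.** The primary mixed model assumes missing at random and imputes nothing after baseline. That is a way to handle gaps; it does not say which window is primary.
- **Age.** SAP 1 says it is read together with the protocol, and the younger band is probably a mislabelled under-65 stratum. That is the likely practical reading, but the sentence sets no precedence. The effect is limited: the stratum term in the primary model is touched only through how the SAP describes it, and the EQ-5D tables are also run for all subjects.

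**Conclusion.** The concern holds on both counts, current text against current text. The SAP must be corrected, chiefly because the conflict is over the definition of the primary endpoint. As written, the primary AUC could go from a 6-day to a 10-day span after an extension recommended by a committee with unblinded data, with no analysis specified for it. The age conflict is narrower: it affects the ordinal-scale model, the age subgroups and the EQ-5D age tables. The number of subjects aged 18 to 49 is not given, so its practical size is unknown.

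No error in power, sample size or alpha is implied. The 40% and 10% figures assume that the SAP's option means Day 11 with Day 1 as baseline; they describe the calendar and not an effect on results. The first-interim trigger also differs: at least 45 randomized in SAP 1.2 and 3, at least 45 treatment completers in Protocol 11.11. The two are compatible, this SAP covers the final analysis, and a separate plan governs the interim, so that is tidying only.

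**What to change.** Amend the SAP before the first formal Part 2 interim, the point by which Protocol 11.3 requires it to be final.

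1. In 1.4 and 4.2, and for the trapezoidal AUC in 4.2.3.1, set the window at baseline to Day 7 whatever the dosing duration.
2. Add the extended-dosing AUC to the secondary endpoints as in Protocol 2.1.2, limited to subjects assigned the longer duration, with its own visit list and contrast.
3. Restate the population in 1.2 as 18 or over (or the legal age of consent), and the younger band in 1.2, 1.5, 2.5, 4.2.4.2 and 4.2.5.3.2 as 18 to <65.
4. As tidying, align the interim trigger in 1.2 and 3 with Protocol 11.11 and confirm that the separate interim plan agrees.

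The cost is a text amendment. Conduct, data collection and sample size do not change.
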